 1.1 If you indicated that personal identifiers will be maintained for future research, provide the following information: a) How the information will be securely handled and stored b) assure confidentiality, and c) who will have access to the identifiers and/or codes

2.0 Describe any additional steps, if any, to be taken to assure that the subjects' identities and any personal identifying information are kept confidential.

ID: IRB#14-001827

View: NEW 10.1 - Study Summary - Research Study

Warning: Save your work at least every 15 minutes by clicking &Save or &Continue.

Study Summary - Research Study -

1.0 Study Materials: As applicable to this study, attach the following:

- Protocol, Dissertation Proposal or Study Plan
- Preliminary Data
- Surveys, Questionnaires or other instruments to be used with study participants
- References

Document Name	Document Version #
LMIL Tables and Figures.docx	0.01
LMIL Bibliography and References cited.docx	0.01
Levomilnacipran proposal 042014.docx	0.01

2.0 *Specific Aims: Indicate the purpose of the research, specifying the problems and/or hypotheses to be addressed.

Specific Aims and Hypotheses:

Primary Aim: To compare the efficacy and generate estimates of the effect sizes on primary and secondary outcomes between the treatment groups in a 12 week double-blind placebo controlled treatment trial with levomilnacipran compared to placebo. Hypothesis 1: We will observe detectable differences in primary (mood) and secondary outcomes (cognition, apathy and quality of life) between the two treatment groups favoring LMIL.

Aim 2: To test whether the two treatment conditions will show no difference in tolerability and safety. We will particularly focus on cardiovascular status (blood pressure, heart rate, ECG changes)

Hypothesis 2: There will not be a difference in the rate of adverse events between the two groups.

Exploratory Aim 3: To compare the patterns of functional and structural connectivity in the two intervention groups. Hypothesis 3: LMIL will lead to improved functional connectivity in brain network activity as measured with resting state (rs-) fMRI, and plasticity in brain macro- and micro-structure as measured with structural MRI and DTI compared to the PBO.

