The rationale for the duration of the interventions, follow up, and blinding procedures: The proposed study is of standard duration for the geriatric population requiring 12 weeks or longer trials to document antidepressant efficacy.

4.0 *Research Design and Methods: Describe in detail the design and methodology of the study.

Subjects: We anticipate screening about 100 subjects to recruit 60 older depressed adults (>60 y.o.) who will be randomized to receive 20-120 mg of levomilnacipran blindly with increment dose titration 20 mg per day -3 days; 40 mg per day-3 days. Based on efficacy and tolerability, we will increase by 40 mg per day each following week 2nd-4th week the maximum recommended doses is 120 mg per day. The comparison group will receive similar blinded titration with matching placebo. Doses of the drugs will be adjusted according to individual tolerability and safety. We expect an attrition rate of about 10% based on our prior experience thus 54 subjects will complete the study. Patients will be assessed pre-treatment; and then weekly during the first four weeks and bi-weekly thereafter. At all visits, clinical ratings of mood, vital signs, and safety will be obtained. Inclusion criteria: 1) The presence of a major depressive disorder diagnosed according to the DSM-IV criteria. 2) A 24-item Hamilton Rating Scale for Depression (HAMD) score of 17 or higher at baseline. 3) Mini-Mental State Exam (MMSE) score > 24.

Exclusion criteria: subjects will be excluded if they had 1) any current and/or lifetime history of other psychiatric disorders (except unipolar depression with or without comorbid generalized anxiety disorder), or 2) recent unstable medical or neurological disorders; 3) any disabilities preventing their participation in the study or in the MRI; 4) diagnosis of dementia; 5) acute suicidality; 6) those with known allergic reactions to milnacipran, uncontrolled narrow angle glaucoma, seizures, poorly-controlled hypertension or ischemic changes on ECG, serotonin syndrome, or the recently used MAOIs within last 4 weeks; 7) ineligible for MRI (e.g., metal in the body or claustrophobia)

Primary outcome will be measured and defined as follows: 1) Remission will be defined as HAMD scores of 6 or less for three consecutive weeks and at week 12; 2) Improvement in depression severity using HAMD scores.

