Neuropsychological assessment (at baseline, at 12 weeks): Our approach to cognitive assessment and analyses is based on our prior work and benefits from input from [name]. We will use a focused test battery developed by [name], assessing domains which have shown impairment in geriatric depression, according to prior research by our group45 and others: 9,46-48 (1) cognitive control, which relates to mental flexibility and inhibition and adjustment of behavior; (2) verbal fluency, which requires strategic searching/organization of verbal knowledge; (3) episodic memory: including explicit memory for verbal and nonverbal information; and (4) information processing speed and attention, including an indices of complex and sustained attention. Most of the measures have 2 or 4 alternate forms that will be important in repeating them during follow up. In addition to the cognitive outcome measures, we will include a brief word reading test, the WAIS-IV Test of Premorbid Functioning (TOPF), a revision of the Wechsler Test of Adult Reading (WTAR),49 to estimate an individual premorbid cognitive functioning. We will conduct a confirmatory factor analysis to assess the goodness of fit of our a priori domain assignments. Finally, we will assess the validity of assignment to composite domains using confirmatory factor analysis. The tests variables derived from each and a priori composite domain assignment: Verbal Fluency (Category and Letter Fluency tests): Cognitive Control (Trailmaking test part B and Stroop Color-Word Interference test); Attention and Processing Speed (Trailmaking test part A; Stroop rapid color and word reading scores (averaged); Digit vigilance d-prime); and Episodic Memory (Rey Auditory Verbal Learning; Brief Visual Spatial Memory tests).

Safety evaluations. Physical examination and vital signs at baseline: pulse rate, systolic blood pressure, and body weight will be obtained at each visit, in addition to a 12-lead ECG at baseline, if any cardiac complaints are present. Laboratory tests (as listed below) will be performed at baseline. The UKU Side Effect Rating Scale,50 a comprehensive rating scale for monitoring adverse events of psychotropic drugs used in clinical trials, will be completed at all visits except screening.

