Hypothesis 1: The primary analyses will focus upon HAM-D24 scores and will be analyzed using general linear mixed model analysis (e.g., SAS PROC MIXED). The two treatment groups will be compared for time course of HAM-D-24 with the initial endpoint EOT at 12 weeks. Covariates may be included in the model as noted above. In addition, likelihood ratio ?2 comparison will examine group differences in remission (HAM-D24 =6) and response (HAM-D24 =10) at EOT. Analyses for the cognitive outcome variables will be akin to those described above for the continuous HAM-D scores. As noted in the Neuropsychological Assessment section, there are four cognitive domains that are being assessed. Of these, the two primary cognitive domains of interest for this proposal are Cognitive Control and Episodic Memory. A separate general linear mixed model as above will be estimated using these two domain scores as dependent variables. The remaining domains, namely Verbal Fluency and Information Processing/Attention will be examined as secondary outcome measures. Apathy will be examined using the AES total score and quality of life using SF-36 scores in similar mixed models.

Hypothesis 2: We will examine adverse events in the two treatment groups. A detailed comparison of the number as well as type of side-effects in the two treatment groups will be conducted using chi-square tests.

Hypothesis 3: LMIL will lead to improved functional connectivity in brain network activity as measured with resting state (rs-) fMRI, and plasticity in brain macro- and micro-structure as measured with structural MRI and DTI compared to the PBO. To address these hypothesis, summary MRI measures (e.g., substructure volume, diffusion metrics) will be included in the GLMMs as "covariates of interest." For whole brain or structure voxel-level or point based measures (e.g., thickness or activation), the GLMMs will be implemented in R (www. R.org). Time (of scan) will be treated as a continuous variable with random intercepts and slopes to account for within-subject correlations between repeated measurements to assess change and interactions amongst the interventions. Difference scores between baseline and 12-week follow-up may be substituted for some analyses. FDR and/or permutation methods will be used to control for multiple anatomic comparisons in whole-brain contexts.

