	information can be found in the attached protocol.	
	•	
2.0	*Provide your assurance that information about serious, unanticipated problems relate incidents and violations) will be reported to the IRB within the time frames specified by	
	Requirements.	
	Agree 🗹 🗹	
	Provide the following information as appropriate to the study:	
3.0	*Are there plans to perform an interim safety analysis?	
	● Yes ○ No	
	• 3.1	
	If yes, describe or indicate where the information can be	
	 found in the attached protocol. Adverse events produced by levomilnacipran may occur. All 	
	- //dverse events produced by leverininacipian may occur. An	

adverse events will be carefully monitored during each visit by using the UKU Side Effect Rating Scale. If any serious medical complication occurs, the PI may discontinue the study medication and may proceed with unblinding the treatment assignment or stopping treatment. We may discover undiagnosed mental and medical conditions in the process of the study, and we will ask for permission by means of a signed Permission to Use Personal Health Information form to report the results of the subjects examination to their primary physician or psychiatrist. An adjustment of the dose of their standing medications may be attempted once seen by their primary care physician. If no improvement occurs or if a prescription of a new medication is required, the study medications will be discontinued.

Discontinuation from the study will be considered if subjects experience:

a. Changes on ECG or in cardiac enzymes indicating cardiac ischemia or a new onset arrhythmia;

b. The development of any severe side-effects on the UKU Side Effect Rating scale rated as 3 or greater.

We will monitor blood pressure and pulse at every visit. We will repeat the ECG once during the trial to ensure safety. If any changes on ECG that signify ischemia occur, we will obtain additional tests of cardiac enzymes to rule out myocardial infarction (MI) (e.g., CK-MB; troponin).

All adverse events will be reported to the subjects and to their primary physicians and the UCLA IRB/ DSMB committee within 10 days of PI�s awareness.

- 1. If a patient demonstrates worsening of their symptoms or no response by week 8 or during follow up (i.e., CGI-I score >3) of treatment, they will be discontinued from the study and referred for appropriate clinical services.

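### Aim 2 makes blood pressure, heart rate and ECG its focus, but the planned analysis compares arms only on recorded side-effects, not on the measured values

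*Combined protocol and SAP*

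**What the plan says.** Section 10.1, item 2.0 (Specific Aims) gives Aim 2 as "To test whether the two treatment conditions will show no difference in tolerability and safety" and adds "We will particularly focus on cardiovascular status (blood pressure, heart rate, ECG changes". The hypothesis under it is narrower: "There will not be a difference in the rate of adverse events between the two groups".

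The whole analysis for Hypothesis 2, in item 6.0, is two sentences: "We will examine adverse events in the two treatment groups" and "A detailed comparison of the number as well as type of side-effects in the two treatment groups will be conducted using chi-square tests". The mixed models in the same item are for HAM-D24, the cognitive domains, AES and SF-36.

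The measurements are planned. Item 4.0 states "At all visits, clinical ratings of mood, vital signs, and safety will be obtained", and its safety evaluations paragraph states "pulse rate, systolic blood pressure, and body weight will be obtained at each visit". Section 15.2, items 3.1 and 4.1, states "We will monitor blood pressure and pulse at every visit", in the context of monitoring individual patients.

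The ECG schedule is given in three ways. The safety evaluations paragraph has a baseline ECG conditional on cardiac symptoms. The medical evaluation paragraph (item 4.0, repeated in section 11.1, item 6.0) has ECG at baseline and at the last visit. Section 15.2 has one repeat during the trial.

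**The concern.** The background in section 10.1 lists tachycardia and palpitations among events occurring twice as often as on placebo, and treats hypertension and orthostatic hypotension as important in older adults. The medical evaluation paragraph gives cardiovascular toxicity as its reason for the ECGs. The risk/benefit statement in section 14.1 argues from measured pulse, blood pressure and ECG in a pilot. The plan therefore already regards measured values as relevant evidence, yet it specifies no randomised comparison of them.

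A drug effect on pulse or pressure can move the average of a whole arm while few patients have anything entered as a side-effect. Such a shift is outside the planned test. Because Hypothesis 2 predicts no difference, an insensitive test leans towards the predicted answer. A cardiovascular analysis added after unblinding would be post hoc.

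**Working it through.** **1. Text check.** I followed each cardiovascular measure from aim to analysis.

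| Measure | Collected | Compared by arm |
|---|---|---|
| Pulse | Every visit | Not stated |
| Systolic blood pressure | Every visit | Not stated |
| ECG | Three differing statements | Not stated |
| Side-effects (UKU scale) | Every visit except screening | Chi-square |

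Visits at weeks 1, 2, 3, 4, 6, 8, 10 and 12 give 8 post-baseline readings. This agrees with the 10 visits in item 5.0 less screening and baseline. The vascular risk factor regressions in item 4.0 concern white matter burden and do not compare treatments.

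**2. The plan's own figure.** Item 6.0 gives a detectable effect of 0.7 SD with 30 per arm, alpha 0.05 and 80% power. Sidedness is not stated; I assume two-sided.

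- Normal approximation: √(2/30) × (1.960 + 0.842) = 0.258 × 2.802 = 0.723.
- Two-sample t: 0.736.

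Both round to 0.7. At exactly 0.70 the t-based power is 76.0%. The figure concerns efficacy; I use 0.7 SD below only as a common yardstick.

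**3. One effect, two analyses.** Take a true shift of 0.7 SD in a vital sign at one time point, 30 per arm.

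*As a mean.* Noncentrality is 0.7/√(2/30) = 2.711 on 58 degrees of freedom, which gives power 76.0%.

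*As a yes/no event.* Assume normal values with equal SD, and an event recorded when a value exceeds a cut-off c set by the placebo rate p0. Then c = z(1 − p0) and the drug-arm rate is p1 = 1 − Φ(c − 0.7). Power is for the Pearson chi-square without continuity correction, from exact binomial probabilities.

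| p0 (assumed) | c | p1 | Power, 30 per arm | Power, 27 per arm |
|---|---|---|---|---|
| 5% | 1.645 | 17.2% | 35% | 31% |
| 10% | 1.282 | 28.0% | 43% | 42% |
| 20% | 0.842 | 44.4% | 53% | 50% |

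The normal approximation at 30 per arm gives 32% to 53%. With 27 completers per arm (54 of 60, from the 10% attrition in item 4.0), the comparison of means has 71% power.

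**4. In clinical units.** The documents give no vital-sign SD. If pulse SD is 8 to 12 bpm, 0.7 SD is 5.6 to 8.4 bpm. If systolic SD is 12 to 18 mmHg, it is 8.4 to 12.6 mmHg.

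**5. What the added estimate would deliver.** For one baseline-adjusted comparison at week 12, the 95% half-width is t × SD × √(1 − ρ²) × √(2/n), with 2n − 3 degrees of freedom. Assume pulse SD 10 bpm and baseline correlation ρ = 0.5.

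- n = 27: 2.008 × 10 × 0.866 × 0.272 = 4.7 bpm.
- n = 20 (assumed): 2.026 × 10 × 0.866 × 0.316 = 5.5 bpm.
- n = 15 (assumed): 2.052 × 10 × 0.866 × 0.365 = 6.5 bpm.

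Using all post-baseline visits should narrow these; I have not quantified by how much.

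**The case against.** Hypothesis 2 and its test agree with each other: one speaks of adverse events and the other compares them. The mismatch is only with the focus sentence under Aim 2. That stands, and it makes this a gap in specification, not a wrong test.

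A reader might infer that cardiovascular safety is not compared between arms at all, or that Aim 2 cannot be addressed. The documents do not support that. Side-effects are compared by number and type, so tachycardia, palpitations or hypertension recorded as side-effects do reach the chi-square tests. What is absent is a comparison of measured values, and any rule for when a measured value becomes a recorded side-effect. Nor do the documents say that equal side-effect counts will be declared proof of cardiovascular safety.

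A reader might also put the loss higher by setting power for a doubled rare event (11% for 5% v 10%, assumed rates) beside power for a pulse shift. Nothing in the documents links those two effects. The like-for-like loss is smaller. It is itself simplified, because a side-effect can be recorded at any of several visits.

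The number left at week 12 is uncertain. Sections 14.1 and 15.2 withdraw patients for worsening or non-response by week 8. Item 4.0 puts drug and placebo at about 30% to 40% each, without naming the outcome, while assuming 10% attrition. Withdrawals under the week-8 rule could exceed that 10%, and week-12 data would then come from patients retained partly because they responded. This limits the precision of any added analysis but does not remove the need for one.

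Finally, the per-visit list names systolic pressure only, and the ECG statements conflict. Both limit what can be analysed.

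**Conclusion.** The concern holds as a modest but real gap between a stated focus and its analysis. Measured pulse, blood pressure and ECG are collected or monitored but have no by-arm comparison; only events recorded as side-effects do. For a 0.7 SD shift at 30 per arm, relying on events lowers power from about 76% to about 35% to 53%. This rests on two-sided alpha of 0.05, normal values with equal SD, a single time point and an assumed placebo event rate of 5% to 20%. Efficacy analyses and the monitoring of individual patients are unaffected. The plan should be amended before unblinding.

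**What to change.** Add to the Hypothesis 2 analysis:

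- **Pulse and systolic blood pressure** (and diastolic, if it is recorded): compare arms over all post-baseline visits with the mixed model already planned for HAM-D24, with the baseline value as covariate. Report arm differences with 95% confidence intervals.
- **Threshold counts:** by arm, the number of patients crossing limits that the investigators set in advance.
- **ECG:** a by-arm tabulation of change, once the schedule statements in section 10.1, item 4.0, section 11.1, item 6.0 and section 15.2 are reconciled.
- **Conclusion:** base the cardiovascular statement of Aim 2 on these estimates together with the side-effect counts.

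This is one reasonable specification among several for a pilot of 60. It costs a few lines of SAP text, a little more analysis work and several further secondary estimates. Pulse and systolic pressure need no new measurements; whether ECG does depends on the reconciled schedule. Report the number of patients contributing at each visit, since week-12 precision may fall below what 27 per arm implies.

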Medical evaluation. All subjects will receive an initial medical assessment including a complete physical examination with neurological and neuropsychiatric examinations, to rule out new-onset medical illnesses that could account for behavioral and cognitive symptoms. All abnormal physical or laboratory findings will be reported to subjects primary physicians with subject consent. If abnormal physical or laboratory results are considered responsible for depression, the subject will be excluded from participation. All subjects will be interviewed about their recent history of psychiatric and medical illnesses, recent psychosocial stressors, current medications, and health status. Because of the concerns of cardiovascular toxicity in older adults- we will do

ECG evaluations at baseline and during last visit.

Dementia and Mild Cognitive Impairment screening. We will screen subjects for possible incipient dementia, and then verify their condition by comparing baseline assessments to the one at follow up. This will include reviewing an extensive history and mental status exam together with corroborating information from the assessment of functional skills. A Mini-Mental State Examination score of < 24 or an established dementia diagnosis will serve as an automatic exclusion criterion. The evaluation for dementia includes: 1) an interview by a psychiatric nurse to identify physical and cognitive limitations; 2) a standard battery of hematologic studies; 3) neurological examination (UPDRS); 3) neuropsychological examination (detailed below); and 4) psychiatric evaluation (SCID-DSM-IV), as detailed above. Adjudication of dementia is based on DSM-IV criteria.51,52 At the consensus conference, additional information will be reviewed (e.g., family history, drug use). Mild Cognitive Impairment diagnosis. Subjects with mild cognitive impairment will not be excluded. We will use performances between -1.5 and -2 (SD) below age and education norms on one of two memory tests used in our cognitive battery according to a widely accepted practice, and control for it in the analyses.

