Randomization and treatment schedule: After all screening and baseline test results are reviewed and eligibility criteria are confirmed, medications will be dispensed if patients continue to meet eligibility criteria and sign the informed consent form. All eligible subjects will be randomized to levomilnacipran or placebo group using a computer-generated random assignment scheme, which assigned subjects in a 1:1 ratio to each group. Randomization will be done prior to subject s being assigned to the groups.

Follow up assessment: The follow up will take place weekly for the first four weeks of treatment, every two weeks for the remainder of the study. Each follow up assessment will include measures of efficacy and safety. The weekly frequency of contact with all subjects will serve as an additional safeguard to monitor worsening of depression, as well as the emergence of side-effects or suicidal ideations.

Study medications and treatment procedures. Subjects will be randomized to: 1) LMIL20-120 mg per day or 2) matching placebo. The allowed range of the drugs according to tolerability and efficacy assessments will be between 20-120 mg per day for LMILN. The dose finding procedures will be only performed in the first four weeks and after that will remain stable until the end of the acute trial, as it worked in our pilot study. We will assess the optimal dose of LMIL based on tolerability and safety in this population. The balance will be maintained between the efficacy and tolerability of medications. If symptoms worsen, the study drug will be tapered and discontinued. Subjects will be referred for clinical care at UCLA or the community. The PI will continue the observation for safety until the appointment is scheduled with the primary psychiatrist. The dose will be titrated according to the titration schedule, including if side-effects are mild or well tolerated and if CGI scores for improvement is 3 or higher. The titration rate is based on the currently recommended titration to achieve the greatest efficacy that may not work for geriatric patients. For that reason, we have safeguards against rapid titration with potential side-effects that will require a slower titration or staying at a lower dose.

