Comorbid anxiety and insomnia will be assessed at baseline visit to decide whether the only allowed concomitant medication allowed in the trial will be lorazepam up to 1 mg/day should be used for treatment of chronic anxiety or insomnia, especially in the habitual benzodiazepine users. We will control for lorazepam use in the statistical analyses. (In all of our pilot studies, the use of lorazepam did not bias the outcomes).

Medical evaluation. All subjects will receive an initial medical assessment including a complete physical examination with neurological and neuropsychiatric examinations, to rule out new-onset medical illnesses that could account for behavioral and cognitive symptoms. All abnormal physical or laboratory findings will be reported to subjects primary physicians with subject consent. If abnormal physical or laboratory results are considered responsible for depression, the subject will be excluded from participation. All subjects will be interviewed about their recent history of psychiatric and medical illnesses, recent psychosocial stressors, current medications, and health status. Because of the concerns of cardiovascular toxicity in older adults- we will do ECG evaluations at baseline and during last visit.

Dementia and Mild Cognitive Impairment screening. We will screen subjects for possible incipient dementia, and then verify their condition by comparing baseline assessments to the one at follow up. This will include reviewing an extensive history and mental status exam together with corroborating information from the assessment of functional skills. A Mini-Mental State Examination score of < 24 or an established dementia diagnosis will serve as an automatic exclusion criterion. The evaluation for dementia includes: 1) an interview by a psychiatric nurse to identify physical and cognitive limitations; 2) a standard battery of hematologic studies; 3) neurological examination (UPDRS); 3) neuropsychological examination (detailed below); and 4) psychiatric evaluation (SCID-DSM-IV), as detailed above. Adjudication of dementia is based on DSM-IV criteria.51,52 At the consensus conference, additional information will be reviewed (e.g., family history, drug use).

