Mild Cognitive Impairment diagnosis. Subjects with mild cognitive impairment will not be excluded. We will use performances between -1.5 and -2 (SD) below age and education norms on one of two memory tests used in our cognitive battery according to a widely accepted practice, and control for it in the analyses.

Randomization and treatment schedule: After all screening and baseline test results are reviewed and eligibility criteria are confirmed by [name]., medications will be dispensed if patients continue to meet eligibility criteria and sign the informed consent form. All eligible subjects will be randomized to levomilnacipran or placebo group using a computer-generated random assignment scheme, which assigned subjects in a 1:1 ratio to each group. Randomization will be done prior to subject sbeing assigned to the groups.

Monitoring of Suicidality.

Assessment and monitoring of suicidal risk will occur at each visit and by phone between visits. We have applied the standard procedures that are required and approved by the UCLA Institutional Review Board. We have employed the same procedures in our ongoing studies of late-life depression since 1995, and have had no suicide attempts among our subjects. We will monitor suicidal ideations using the third item of the Hamilton Depression Scale during each visit to the site. Monitoring for SI will be done at each visit independent of the outcome assessment. The blind rater will be instructed to inform the PI of scores = 3. Subjects with active suicidal ideations with or without a plan, HAMD-24 score = 3, will be excluded from participation. We will call subjects between visits to monitor suicidal ideations. We will encourage participation of their family members in the study who will be encouraged to call the patient and the study staff in case suicidal ideations emerge during the study. In the presence of persistent suicidal ideations, subjects will be discontinued from the study and referred to clinical services or to the community for treatment.

ID: IRB#14-001827

View: NEW 11.2 - Characteristics of Study Population

Warning: Save your work at least every 15 minutes by clicking & Save & or & Continue.

7	k all that apply: 0 to 6 years 7 to 11 years 12 to 17 years
7	7 to 11 years
	·
	12 to 17 years
	12 to 17 years
	17 or younger in California who can consent for themselves - see note below
	17 or younger outside California who can consent for themselves - see note below
*	18 years or older
4	
NOTE	=.

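### The Safety evaluations paragraph limits the baseline 12-lead ECG to subjects with cardiac complaints, contradicting the unconditional baseline ECG in Medical evaluation

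*Combined protocol and SAP*

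**What the plan says.** **The conditional rule.** Section 10.1 item 4.0, Safety evaluations, sets out the physical examination and vital signs and then adds the ECG: "in addition to a 12-lead ECG at baseline, if any cardiac complaints are present". The paragraph does not mention an ECG at the last visit.

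**The unconditional rule.** Medical evaluation, in the same item, commits to "ECG evaluations at baseline and during last visit". Section 11.1 item 6.0 repeats the text with its reason: "Because of the concerns of cardiovascular toxicity in older adults- we will do ECG evaluations at baseline and during last visit". Both paragraphs begin by saying that the initial medical assessment applies to all subjects, and neither mentions cardiac complaints.

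**What relies on the ECG.**
- The exclusion criteria in Section 10.1 item 4.0 and Section 11.1 item 5.0 include "poorly-controlled hypertension or ischemic changes on ECG".
- The randomization paragraph in Section 10.1 item 4.0 fixes the order of events: "After all screening and baseline test results are reviewed and eligibility criteria are confirmed, medications will be dispensed". Section 11.1 item 6.0 does the same.
- Section 15.2, items 3.1 and 4.1, lists as grounds for considering discontinuation: "Changes on ECG or in cardiac enzymes indicating cardiac ischemia or a new onset arrhythmia". Both items also state: "We will repeat the ECG once during the trial to ensure safety".
- Aim 2 (Section 10.1 item 2.0) names ECG changes, with blood pressure and heart rate, as a focus of the safety comparison.

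**The concern.** Two current rules for the same procedure differ, and the plan gives no order of precedence. The conditional one stands under the safety heading, where study staff would naturally look for the schedule of safety procedures.

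The stakes are eligibility and subject safety. An exclusion that depends on an ECG finding works only if there is an ECG. A discontinuation criterion built on change and new onset works best with a tracing from before treatment. The plan itself gives reasons to expect cardiac findings:
- Section 10.1 item 3.0 lists tachycardia and palpitations among the commonest adverse events seen twice as often as on placebo, so a subject with no complaint at baseline may develop one on treatment.
- Section 14.1 item 4.0 says that most subjects in the group's milnacipran pilot had a history of cardiovascular disease or hypertension, so an old ECG abnormality without a current complaint is plausible in this population.

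The conditional rule would leave such subjects without a reference tracing.

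**Working it through.** No formula applies: the point does not depend on sample size, power or alpha. The check is a comparison of every ECG statement in the document.

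**Step 1. What the conditional sentence can mean.** Read literally, the clause on cardiac complaints attaches to the baseline ECG, because nothing separates the two. The other possible reading is an ECG at baseline and a further one if complaints arise. That needs a conjunction that is not there. The sentence is loosely built in any case, since it places vital signs both at baseline and at each visit. The literal reading conflicts with Medical evaluation. The other reading does not conflict, but it is not what the sentence says.

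**Step 2. The rules side by side, for a subject with no cardiac complaints.**

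| Question | Safety evaluations, as written | Medical evaluation (10.1 and 11.1) |
|---|---|---|
| ECG at baseline? | Not required | Required |
| ECG at last visit? | Silent | Required |

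The contradiction is confined to baseline. On the last visit, Safety evaluations omits the ECG but does not rule it out.

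**Step 3. What each dependent provision needs.**
- *Ischemic-ECG exclusion, checked before dispensing.* This needs an ECG before study medication. It is met under Medical evaluation. Under the literal Safety evaluations rule, a complaint-free subject has no study ECG on which to check it.
- *Discontinuation for ECG change or new-onset arrhythmia.* This needs a reference tracing, or a substitute such as medical history. Medical evaluation supplies the tracing; the conditional rule does not.
- *Repeat ECG in Section 15.2.* To repeat an ECG presupposes a first one, which again fits Medical evaluation.
- *Aim 2 focus on ECG changes.* A change is measured from a baseline.

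All four fit the unconditional rule, and none fits the literal conditional rule for complaint-free subjects.

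**Step 4. Effect on the analysis.** Hypothesis 2 in Section 10.1 item 6.0 compares the number and type of side effects between arms by chi-square tests. No ECG change score is tested, so no prespecified test is altered.

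**Step 5. How many subjects.** The plan is to randomize 60. The documents do not give the share expected to report cardiac complaints at baseline, so the number exposed to the conditional rule cannot be computed.

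**The case against.** The strongest reply is that the rest of the plan already settles the matter. The unconditional ECG is stated twice, with a reason, in paragraphs addressed to all subjects. The exclusion, the eligibility check before dispensing and the word repeat in Section 15.2 all assume it. Against them stands one trailing clause in a poorly built sentence that may simply have lost an *and*. Someone who follows Medical evaluation for the last-visit ECG has read its baseline commitment too. On this view the defect is editorial.

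Much of this stands. The unconditional rule is probably the intent, and the harm arises only if staff follow Safety evaluations instead. But evidence of intent is a reason to correct the sentence; it does not remove the conflict.

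Three stronger readings are tempting, and the documents do not support them.
- *Complaint-free subjects will have no baseline ECG.* A reader might infer this from Safety evaluations alone. Medical evaluation says otherwise twice, and no text gives Safety evaluations precedence.
- *Without a baseline tracing, a later abnormality cannot be classified.* This is too absolute. Section 15.2 backs ischemic ECG changes with cardiac enzymes, Medical evaluation takes a recent medical history and a full physical examination, and pulse is recorded at every visit. Classification becomes harder, not impossible.
- *A fixed number of tracings per subject is lost.* Any such count assumes that the single repeat ECG in Section 15.2 is the last-visit ECG. The plan does not say so; it could be a separate on-treatment check.

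**Conclusion.** The point holds as a contradiction between two current safety rules. Safety evaluations, read as written, makes the baseline 12-lead ECG depend on cardiac complaints; Medical evaluation does not, and the exclusion, discontinuation and Aim 2 provisions assume a baseline tracing in everyone. If the conditional rule were followed, complaint-free subjects would begin study medication without a study check of the ischemic-ECG exclusion, and their later ECG findings would be harder to interpret.

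This rests on the literal reading of the sentence and, for any harm, on staff acting on it rather than on Medical evaluation. The consequence is for eligibility and subject safety only. It should be corrected, because the conditional rule gives a worse result if followed and the correction costs almost nothing. The wording conflict is certain; that any subject would actually go without a baseline ECG is not.

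**What to change.** Reword the ECG clause of Safety evaluations in Section 10.1 item 4.0 to say three things:
1. Every subject has a 12-lead ECG at baseline, reviewed before medication is dispensed.
2. Every subject has a 12-lead ECG at the last visit, as Medical evaluation already provides.
3. Additional ECGs are done if cardiac complaints arise.

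Leave the repeat-ECG sentence in Section 15.2, items 3.1 and 4.1, as it is. At most, ask the sponsor whether that repeat is the last-visit ECG or a separate on-treatment check. Tying it to the last visit without that answer could remove an intended safety tracing.

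The cost is one wording change. It requires no scheduled ECG beyond those Medical evaluation already commits to; any extra tracing would be prompted by a subject's complaints.
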